6.4.2 Part 2 PD Cohort

Although the PK parameters will be presented as for Part 1 (according to Treatment dose group) the C_{max} and AUCs will also be formally analysed to evaluate the relationship between the ascending dose groups (Dose-proportionality as in Figure 1). In addition to the patients from the four treatment groups in Part 2 (5mg, 10mg, 20mg and 40mg), the 80mg group of PD patients from Part 1 will be included.

This will involve an ANOVA power model using the log transformed individual patient derived parameters as an explanatory variable and with Treatment dose group as the dependent fixed effect. In the event of demonstrating an overall statistically significant difference, comparisons between all pairs of means will be performed using the Scheffe method. LSmeans point estimates with 95% CIs derived will be presented after back transformation (exponentiation) of all pairwise differences between doses as ratios (%). Significant differences ($p < 0.05$) in the ratio of any two doses will be declared if the 95% confidence interval excludes 100%.

The regression slope (Figure 1) of the log transformed PK parameter against log Dose represents the power model ($\log(AUC) = a + b * (\text{Dose})$) where 'a' represents the intercept and 'b' the coefficient for linear slope). Therefore, a 90% confidence interval for the estimate of the slope excluding $b=1$ will indicate significant departure from linearity.

Figure 1: Dose Proportionality (Log PK Parameter vs Log Dose)

For the dose difference analysis, all dose group estimates will be presented as LS means with 95% CIs after back transformation of the log values and all pairwise comparisons with the lowest dose will be presented as ratios of LS means (%) with 95% confidence intervals. These will be presented graphically.

For both the Differences between doses and Dose proportionality analyses of the C_{max} and AUC parameters summaries of the model applied with Mean square error, Degrees of freedom, F statistic and resulting p-value for each model parameter will be displayed.

For Dose proportionality the coefficient of the linear slope (b) will be presented as a point estimate with 90% CI together with plots of $\log C_{max}$ vs Dose and $\log AUC$ vs Dose.

7. Presentation.

As each cohort completes (Part 1 AD, Part 1 PD, and Part 2 PD) these data will be unblinded and the pharmacodynamics (Biomarkers in CSF and plasma), efficacy, and safety will be evaluated and presented accordingly.

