Once all patients in Part 2 have completed, the PK data and infective particle and exosomes data from all three cohorts will be made available and analysed separately.

Summaries will be presented by cohort and treatment, visit and time recorded as appropriate.

The table below summarises the schedule for presentation of each cohort's statistical report output:

Analysis	Cohort	Deliverables
1	Part 1 – PD Patients (14)	Disposition Tables and Listings Biomarker* Tables, Figures and Listings Functional/cognitive Tables, Figures and Listings Safety Tables and Listings
2	Part 1 – AD Patients (14)	Disposition Tables and Listings Biomarker* Tables, Figures and Listings Functional/cognitive Tables, Figures and Listings Safety Tables and Listings
On completion of Part 2:		
3	PD Patients (54) – including 14 PD patients from Part 1 and 40 PD patients from Part 2	Disposition Tables and Listings Biomarker* Tables, Figures and Listings Functional/cognitive Tables, Figures and Listings Safety Tables and Listings
4	PD Patients (50) – including ten 80mg PD patients from Part 1 and forty PD patients (5mg, 10mg, 20mg and 40mg) from Part 2 AD Patients (10) – 80mg patients from Part 1 All patients (68) from Part1 and Part 2	PK analyses Tables, Figures and Listings PK analyses Tables, Figures and Listings Infective Particles in CSF: Tables, Figures and Listings Exosomes in plasma: Tables, Figures and Listings

*Biomarker results (excluding infective particles and exosomes) from assays conducted in Part 1 will be evaluated by the Sponsor and will inform the choice of assays and subsequent output from Part 2

NB: Infective particles and exosomes biomarker data will not be presented until after the completion of Part 2

Detailed ‘table shells’ for Part 1 and Part 2 will be produced to accompany this SAP. These not only describe table layout but table numbering formats and also the level of accuracy (number of decimal places) to be described in each table.

The following described tables and figures will be included in the statistical report.

7.1 Study Status.

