7.4 Pharmacokinetics

All PK statistical analysis will be carried out after the completion of Part 2.

For each cohort, the plasma concentration data and derived pharmacokinetic parameters of Posiphen will be listed by treatment group, patient and time point.

For each cohort, the actual values and derived pharmacokinetic parameters will be summarised using descriptive summaries (arithmetic mean, standard deviation, coefficient of variation, mean, median, minimum, maximum and number of observations) for each treatment dose group. If appropriate, geometric means will be displayed in addition to the arithmetic mean (Actual drug concentrations: Table 14.5.1; and, Parameter summaries: Table 14.5.2). Supporting plots will display drug concentration over the 6-hour confinement period by treatment group (Figures 14.5.1, Template 6), together with parameter summary Geometric LS Means +/- 90%CI (Figures 14.5.2, Template 7).

For Part 2, the statistical analysis of the Differences between doses for all Parkinson patients (including 5mg, 10mg, 20mg and 40mg from Part 2, and 80mg from Part 1) and Dose proportionality of both C_{max} and AUC parameters will include details of the model applied with Mean square error, Degrees of freedom, F statistic and resulting p-value for each factor or model parameter. For the dose difference analysis, all dose group estimates will be presented LS means with 95% confidence intervals after back transformation of the log values and all pairwise comparisons between doses will be presented as ratios of LS means (%) with 95% confidence intervals (Table 14.5.3). These will also be plotted as shown in Section 6.4.2 (Figure 14.5.3).

8. References.

ICHE9 “Statistical Principles For Clinical Trials” February 1998.
ICHE8 “General Considerations For Clinical Trials” July 1997.

9. Finalisation of Statistical Analysis Plan.

The statistical analysis plan, and all relevant table shells will be finalised before the database lock of the Part 1, PD patient cohort.

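### The pairwise PK dose comparisons use Scheffe where Tukey-Kramer would be tighter, do not say whether the decision intervals are adjusted, and give two different comparison sets

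*SAP*

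**What the plan says.** SAP section 6.4.2 sets out a dose-difference analysis of log-transformed Cmax and AUC. It covers the four Part 2 doses (5, 10, 20 and 40 mg), and "the 80mg group of PD patients from Part 1 will be included". The analysis schedule in SAP section 7 gives the numbers for the PD pharmacokinetic analysis: "including ten 80mg PD patients from Part 1 and forty PD patients (5mg, 10mg, 20mg and 40mg) from Part 2".

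The procedure is stated in three steps:

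- The pairwise step is conditional: "In the event of demonstrating an overall statistically significant difference", then "comparisons between all pairs of means will be performed using the Scheffe method".
- The estimates follow: "LSmeans point estimates with 95% CIs derived will be presented after back transformation (exponentiation) of all pairwise differences between doses as ratios".
- The decision rule comes next: a significant difference (p < 0.05) "in the ratio of any two doses will be declared if the 95% confidence interval excludes 100" per cent.

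No sentence says whether these 95% intervals carry the Scheffe multiplier.

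Later in the same section, the set to be presented is "all pairwise comparisons with the lowest dose". Section 7.4 instead says "all pairwise comparisons between doses will be presented as ratios of LS means (%) with 95% confidence intervals", again without naming an adjustment.

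Dose proportionality itself is judged separately in 6.4.2, by whether the 90% confidence interval for the power-model slope excludes 1.

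**The concern.** There are three related points.

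1. **Efficiency.** Scheffe controls error over all linear contrasts of the five means. The SAP plans only pairs, so part of the interval width protects contrasts that nobody intends to examine.
2. **Unspecified adjustment.** The rule that declares two doses different rests on a 95% interval whose multiplier is not stated. Scheffe and ordinary t intervals differ by about 60% in width, so a moderate difference can be significant under one and not under the other. If the text leaves this open, it may be settled when the output is programmed, with the data available.
3. **Comparison set.** All pairs means ten comparisons; against the lowest dose means four. The set determines which multiplicity method is appropriate, so the first two points cannot be closed until it is fixed.

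At stake is whether neighbouring doses are reported as giving different exposure. No sample size or safety decision depends on it.

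**Working it through.** The documents give no critical value, interval width or power for these comparisons, so there is no stated figure to reproduce.

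**Inputs**

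- Dose groups: k = 5 (5, 10, 20, 40, 80 mg), from SAP 6.4.2.
- Patients: 10 per group, N = 50, from the schedule in SAP section 7. All are assumed evaluable.
- Pairs: 5 × 4 / 2 = 10. Error degrees of freedom: 50 − 5 = 45.
- Two-sided alpha 0.05, from the 95% interval and p < 0.05 in 6.4.2. The level of the overall F test is not stated; 0.05 is assumed.
- Equal variances on the log scale are assumed.

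**Multiplier on the standard error of a log ratio**

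| Method | Formula | Value |
|---|---|---|
| Scheffe | √[4 × F(0.95; 4, 45)] = √(4 × 2.579) | 3.212 |
| Bonferroni, 10 pairs | t(1 − 0.05/20; 45) | 2.952 |
| Tukey | q(0.95; 5, 45)/√2 = 4.018/√2 | 2.841 |
| Dunnett, 4 comparisons with the lowest dose | simulated | 2.53 |
| Ordinary 95% interval | t(0.975; 45) | 2.014 |

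- Scheffe against Tukey: 3.212/2.841 = 1.130, so 13% wider.
- Scheffe against Bonferroni: 3.212/2.952 = 1.088, so 9% wider.
- Scheffe against ordinary: 3.212/2.014 = 1.595, so about 60% wider.
- With 6 to 10 evaluable patients per group, the Scheffe-to-Tukey excess stays at 13.0% to 13.1%.

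**Family-wise error over the ten pairs** (simulation)

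| Interval | All doses equal, no F gate | All doses equal, behind F gate | One dose far away, other four equal, gate open |
|---|---|---|---|
| Scheffe | 1.9% | 1.9% | 1.3% |
| Tukey | 5.0% | 4.0% | 3.3% |
| Ordinary | 27.6% | 5.0% | 19.8% |

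The SAP has the gate, so the middle column, not the first, describes its procedure when all doses are equal. The gate adds nothing to Scheffe, because no Scheffe comparison can be significant unless the F test is.

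**Is the gate likely to be open?** The doses span 80/5 = 16-fold. If exposure is proportional to dose, the overall F test is significant with probability above 99.99% for every between-subject CV tried from 30% to 120%. These CVs are assumptions, because the documents give none for Cmax or AUC. In practice the pairwise rule would therefore decide.

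**Does the choice change a result?** Adjacent doses differ two-fold. Under exact proportionality the expected t for one doubling is ln 2 / (σ√(2/10)), with σ = √ln(1 + CV²).

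- CV 50%: σ = 0.472, standard error 0.211, expected t = 0.693/0.211 = 3.28.
- CV 70%: σ = 0.631, standard error 0.282, expected t = 0.693/0.282 = 2.45.

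The expected t lies between 2.01 and 3.21 for CVs of about 51% to 90%. The chance of declaring one given adjacent pair different is:

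| Assumed CV | Ordinary | Tukey | Scheffe |
|---|---|---|---|
| 50% | 89% | 67% | 53% |
| 70% | 67% | 36% | 24% |

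**The case against.** A reader might infer that 6.4.2 contains two conflicting decision rules, one by Scheffe and one by an unadjusted interval. The text does not establish that. The Scheffe sentence, the interval sentence and the significance sentence are consecutive and can be read as one procedure. If the intervals are Scheffe intervals, exclusion of 100% and Scheffe significance are the same rule. A conflict arises only if ordinary intervals are meant. What remains is an unstated adjustment. The table shells in SAP Appendix 1 may label the interval, but they are not among the documents reviewed.

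A reader might also take 27.6% as the error rate of the plan under ordinary intervals. It is not, because that figure ignores the overall F test. The gate does not protect when some doses differ and others do not, which is where the 19.8% arises. In fairness, if exposure rises steadily with dose, no two doses truly have a ratio of 100%, and false positives are then a small concern; interval width and power matter more.

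It is fair, too, that Scheffe is a valid method and that the trial is exploratory. Using it is a loss of efficiency, not an error. The 13% holds against Tukey specifically. Nor was the sample size set on these contrasts, so translating the loss into extra patients would have no bearing on the design.

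Finally, Tukey is not automatically the right replacement. If only comparisons with the lowest dose are intended, Tukey (2.84) is itself wider than Dunnett (2.53). This objection stands, and it makes the comparison set the first thing to settle.

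**Conclusion.** The point holds as a low-severity, free improvement. The contradiction in the comparison set is explicit in the text and needs no interpretation. The missing statement about adjustment is a real gap, because the two readings use multipliers of 3.21 and 2.01 and can lead to different reports for neighbouring doses at plausible but assumed CVs. If all pairs are intended, Scheffe costs about 13% in interval width on the log scale compared with Tukey-Kramer, with no compensating benefit, since no other contrasts are planned.

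These figures assume 10 evaluable patients in each of five groups, equal log-scale variances and an F test at 0.05. The dose-proportionality conclusion from the slope is unaffected.

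**What to change.** 1. Choose one comparison set, all pairs or lowest dose only, and state it identically in SAP 6.4.2 and 7.4.
2. If all pairs, replace Scheffe with Tukey-Kramer. If lowest dose only, use Dunnett.
3. State that the 95% confidence intervals in the significance rule, and those tabulated and plotted under 7.4, are these adjusted intervals.
4. State the level of the overall F test if it is kept. Neither Tukey-Kramer nor Dunnett needs it; keeping it in front of Tukey lowers the family-wise error under equal doses from 5.0% to 4.0%.

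The cost is one option in the SAS call and a few sentences in the SAP, with matching labels in the table shells. It needs no new data and no extra patients. Under all pairs, the only thing given up is Scheffe's cover for non-pairwise contrasts, and none are planned.

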AUC_{0-t}	Area under the plasma concentration-time curve from time-zero to the time of the last measurable concentration.	Calculated using the linear trapezoidal rule $((t_2 - t_1) * (C_1 + C_2) / 2)$ during the ascending portion of the curve and the log-trapezoidal rule $((t_2 - t_1) * (C_2 - C_1) / \ln(C_2 / C_1))$ during the descending portion of the curve.
$AUC_{0-\infty}$	Area under the concentration time curve from time-zero extrapolated to infinity	$AUC_{inf} = AUC_{last} + \frac{C_{last}}{\lambda_z}$
CL/F	Apparent systemic clearance	$CL / F = \frac{Dose}{AUC_{inf}}$

*NB: Parameters used in derivations but not presented in data summaries.

For the purpose of calculating AUCs when two consecutive plasma concentrations are below the lower limit of quantification (LLOQ) after t_{max} , all subsequent values will be excluded from derivations. However, single 'embedded' missing values will be included in the derivations with extrapolation between the items.

5.5 Missing Data.

All possible efforts will be made to ensure complete data collection and no imputation of data will be performed.

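### The pairwise PK comparisons in SAP 6.4.2 test equal raw exposure (100%) rather than dose-proportionality, so they cannot show where proportionality fails

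*SAP*

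**What the plan says.** SAP 6.4.2 states that Cmax and the AUCs will be "formally analysed to evaluate the relationship between the ascending dose groups (Dose-proportionality as in Figure 1"). The doses are 5, 10, 20 and 40 mg from Part 2 plus the 80 mg PD group from Part 1 ("In addition to the patients from the four treatment groups in Part 2 (5mg, 10mg, 20mg and 40mg), the 80mg group of PD patients"). The schedule of reports in SAP section 7 gives the numbers: "including ten 80mg PD patients from Part 1 and forty PD patients (5mg, 10mg, 20mg and 40mg) from Part 2", which is 10 per dose and 50 in all.

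The section then describes the method as an ANOVA power model "using the log transformed individual patient derived parameters", with dose group as the factor. "In the event of demonstrating an overall statistically significant difference", all pairs are compared by Scheffé's method and back-transformed to ratios. A significant difference "will be declared if the 95% confidence interval excludes 100" percent.

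Neither document mentions dividing by dose. Table 5 in SAP 5.4 defines the parameters in raw form; AUC, for example, is the "Area under the plasma concentration-time curve from time-zero to the time of the last measurable concentration".

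Two further statements matter. First, SAP 6.4.2 has a separate criterion: a 90% confidence interval for the slope of log parameter on log dose that excludes 1 indicates departure from proportionality. Second, SAP 6.4.2 and 7.4 name a dose-difference analysis and a dose-proportionality analysis as two items. SAP 7.4 adds that "all pairwise comparisons between doses will be presented as ratios of LS means", without repeating the 100% rule.

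**The concern.** The ANOVA and pairwise ratios follow directly from a sentence about dose-proportionality, so a reader of the report will take the pairwise results as evidence on it. But comparing raw exposure at two different doses with 100% asks whether the doses give the same exposure. Over a 16-fold dose range that question is largely settled before the data arrive.

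PK is a primary outcome of the trial, and both documents cite support for dose-proportionality analyses among the reasons for ten patients per dose. Protocol 3.2 also gives grounds to expect a break rather than a smooth power law. It describes Cmax in the multiple-dose study as rising disproportionately, with 110, 134 and 2101 after repeated 20, 40 and 60 mg doses. Those values carry an AUC unit and come from four-times-daily dosing, so they only illustrate the pattern. Still, a 1.2-fold rise followed by a nearly 16-fold rise is not something one exponent can describe.

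**Working it through.** The plan gives no operating characteristics for this rule, so there is no figure to reproduce. The check is what the rule does when exposure is exactly dose-proportional.

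**Inputs from the SAP.** Five doses (5, 10, 20, 40, 80 mg), n = 10 each, residual df = 5 × 9 = 45, Scheffé limits, two-sided 95% intervals.

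**Assumptions.** Log-normal parameters with a common residual SD; overall F test at 0.05. The documents give no CV for Cmax or AUC, so a range of 30% to 150% is used.

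**Reference value.** If exposure ∝ dose^b, the true ratio for doses d1 and d2 is (d2/d1)^b. A ratio of 100% requires b = 0. Proportionality (b = 1) gives 200%, 400%, 800% and 1600% for dose ratios of 2, 4, 8 and 16.

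**Width of the interval at CV 50%.**
- σ = √ln(1 + 0.5²) = 0.472.
- SE of a log ratio = 0.472 × √(2/10) = 0.211.
- Scheffé multiplier = √(4 × F(0.95; 4, 45)) = √(4 × 2.579) = 3.21.
- Half-width = 3.21 × 0.211 = 0.678, a factor of e^0.678 = 1.97.

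An observed ratio above about 197% is therefore declared significant. With a true ratio of 200%, an adjacent pair is declared about half the time. For 80 versus 5 mg the typical interval is 1600/1.97 to 1600 × 1.97, or 812% to 3153%. It excludes 100% by a wide margin and comfortably contains the proportional value of 1600%.

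**Simulation of the rule as written, exact proportionality, 20,000 trials per row (% of trials declared significant).**

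| CV | Overall F | 2× pairs | 4× | 8× | 16× |
|---|---|---|---|---|---|
| 30% | 100 | 98 | 100 | 100 | 100 |
| 50% | 100 | 53 | 100 | 100 | 100 |
| 70% | 100 | 24 | 95 | 100 | 100 |
| 100% | 100 | 10 | 70 | 99 | 100 |
| 150% | 99.9 | 5 | 37 | 85 | 99 |

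In the same data the slope rule rejects b = 1 in about 10% of trials, as a 90% interval should.

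**Same simulation on log(parameter/dose).** The overall F test is passed in about 5% of trials, at least one Scheffé pair is declared in about 2%, and any single pair in 0.2 to 0.3%, at every CV. On this scale 100% is the proportionality null.

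**Locating a break.** Set the 20 to 40 mg step to 134/110 = 1.22 (Protocol 3.2, repeated dosing) and keep the other three steps at exactly 2.

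| CV | Rule | 20→40 mg (not proportional) | Each proportional step |
|---|---|---|---|
| 30% | raw against 100% | about 5% | about 98% |
| 30% | dose-normalised | about 71% | 0.2–0.3% |
| 50% | raw against 100% | about 1.5% | about 53% |
| 50% | dose-normalised | about 21% | about 0.2% |

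The raw rule declares the proportional steps and passes over the one that is not.

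**What the slope shows in that example.** With equally spaced log doses, the expected slope is 0.7 + 0.3 × log2(1.22) = 0.7 + 0.3 × 0.285 = 0.785. At CV 30%, σ = √ln(1 + 0.3²) = 0.294 and the SE is about 0.294/√(10 × 10 × (ln 2)²) = 0.042. The 90% interval is then roughly 0.785 ± 1.68 × 0.042, or 0.71 to 0.86. The slope correctly reports a departure, but describes it as 2^0.785 = 1.72-fold exposure per doubling at every step, which is true of none of them.

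**The case against.** The strongest reply is that the SAP already tests proportionality in the same section, through the slope against 1. That test needs no normalisation. The SAP also names the dose-difference analysis separately, and for that analysis equal exposure is a legitimate null. Under proportionality, 40 mg and 20 mg do give different exposures, so declaring them different is correct. The percentages in the first table are then power to detect real differences.

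All of this stands, and it rules out two readings that a reader might infer. One is that the trial has no valid test of proportionality; the slope criterion is such a test. The other is that the rule has a false-positive rate of 53% or 98%; no false positive occurs, because the exposures differ. It is also fair that SAP 7.4 only presents the ratios and does not repeat the 100% rule, that the study is exploratory, and that Protocol 6.4 makes the proportionality assessment optional.

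The reply does not remove the point. SAP 6.4.2 introduces the pairwise ANOVA as part of evaluating proportionality and calls it a power model, so its results will be read that way. As a pure dose-difference test, its overall result and its widest comparison are close to foregone conclusions under proportionality. And the slope, though valid for the overall question, does not say between which doses proportionality fails.

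**Conclusion.** The point holds in a limited form. The pairwise rule tests equality of raw exposure, is placed under dose-proportionality, and cannot inform on it. Under exact proportionality the overall test is passed in 99.9 to 100% of trials and 80 versus 5 mg is declared different in 99 to 100%, across assumed CVs of 30 to 150%. Adjacent pairs are less certain, from 98% at CV 30% down to 5% at CV 150%, so it would be wrong to say that every pair is always significant.

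The loss is the ability to locate a break in proportionality. In the worked example at CV 30%, the non-proportional step is declared in about 5% of trials on raw ratios and about 71% on dose-normalised ratios. The gain shrinks as variability grows (about 21% at CV 50%), so with ten per dose the normalised ratios help but are not decisive. The CVs are assumptions, and the break is an illustration built on two earlier figures. No treatment or stopping rule in the documents depends on the pairwise result. This is an analysis to correct before the PK report, and it does not threaten the trial.

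**What to change.** In SAP 6.4.2, for the dose-proportionality evaluation, run the ANOVA and the Scheffé pairwise ratios on log(Cmax/dose) and log(AUC/dose), so that a ratio of 100% means proportional.

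If the raw ratios are kept for the dose-difference analysis, show them with their confidence intervals beside the corresponding dose ratio (200% to 1600%). Either drop the declaration based on 100% or state that it concerns raw exposure only. In both cases, state that overall proportionality is judged by the slope and its 90% interval. Since the slope then carries that conclusion, align its displayed equation, which shows dose, with the text, which says log dose.

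Carry the same wording into SAP 7.4 and the matching table shell. The cost is one derived variable, a few lines of SAP text, and one further set of pairwise output if the raw ratios are also reported. No new data are needed.

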3.2 Summary of Clinical Findings

Three Phase 1 studies have been conducted with Posiphen ([IB 2019](#)). The first was a single ascending dose (SAD) study in healthy volunteers; the second was a multiple ascending dose (MAD) study in healthy volunteers, and the third one was a pharmacokinetic

(PK)/pharmacodynamic study of CSF obtained from mild cognitively impaired participants (Protocol QR12001).

In the MAD trial, Posiphen was administered orally in doses of 20, 40, and 60 mg 4 times a day (QID). The first two treatments were administered for 7 days, and the third, for 10 days. Single doses were given on the first and last day to determine the pharmacokinetics of the drug. In general, the drug was well tolerated, resulting in no serious or severe adverse events and only one premature discontinuation, a subject in the 60 mg group discharged because of nausea, vomiting, dizziness and “feeling warm.” The incidence of adverse events, all either mild or moderate severity, also occurred with similar frequency in the placebo group. The most common AEs were dizziness, headache, and nausea/vomiting.

Posiphen was absorbed rapidly after oral administration, achieving maximum plasma and CSF concentration (C_{max}) within 1.2 - 1.5 hours. For the 40 and 60 mg doses, with fully defined plasma profiles, the mean terminal $t_{1/2}$ ’s were 3.80 ± 0.88 and 5.23 ± 1.24 hours, respectively after a single dose and 3.53 ± 1.03 and 4.104 ± 0.91 hours, respectively, after repeat dosing. The half-life ($t_{1/2}$) of the plasma concentrations at the lower doses could not be calculated accurately. The C_{max} increased disproportionately with dose (24, 144, and 2310 ng.h/mL after a single dose of 20, 40, and 60 mg, respectively and 110, 134, and 2101 ng.h/mL after multiple doses of 20, 40, and 60 mg, respectively).

In the proof of mechanism of action study (Protocol QR12001), the PK of Posiphen was measured after 10 days of administration (4x60 mg) over 6 hours in CSF and plasma of the AD participants. The pharmacodynamics of a number of biomarkers was compared for 6 hours before the first dose at day 0 and after the last dose at day 11 of Posiphen administration. We found that the plasma concentrations of Posiphen overlapped with the plasma concentrations found in the MAD study. In this study, the N1 metabolite reached about 10 to 15%, while the level of the N8 metabolite reached about 20 to 25% of the Posiphen levels measured in plasma.

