6.2 Power and Sample Size Determination

This is an exploratory study to assess safety, tolerability and pharmacokinetics for Early AD and Early PD patients in addition to investigating pharmacodynamics and efficacy focusing on target engagement, pathway engagement and functional/cognitive measures. 10 patients per dose group provides enough data to characterize the PK of Posiphen as well as adequately supporting potential dose proportionality analyses.

Due to the sample size computation below, we will state that sAPP α , sAPP β and aSYN were given specific consideration in deciding the need to have 10 Posiphen patients in each treatment group given their specific importance in the emergence and progression of AD and PD. The statistical background and rational for having 10 Posiphen patients in each treatment group to have a meaningful interpretation of sAPP α , sAPP β and aSYN data are outlined below.

The statistical evaluation of our previous study in MCI patients with soluble APP α and β levels measured in spinal fluid before and after Posiphen administration (Protocol QR12001) can be used to power this study ([name] 2012). All assay data collected were analyzed using a repeated measure mixed model analysis of variance. The model included Day (Day 11/Day0) as a fixed effect, Time (9 time points per person between 0 and 6 hours) as a repeat measure effect

and Patient (18 samples per person total) as a random effect. Data are presented as means \pm SEs. The statistical evaluations were undertaken by Data Magik (Salisbury, UK).

Human biomarker	CSF % of time 0	SE	p Value
(A) AD biomarkers			
sAPP α	-59.9%	0.231	0.0006
	-34.1%	0.659	0.0661
sAPP β	-57.7%	0.361	0.0001
	-34.0%	1.516	0.0901

Analysis of sAPP α and β using type, day and id as variables shows:

	type	time	N	delta_MN	delta_SE	delta_SD	%chng_MN	%chng_SE	z	pv
1	alpha	1.5h	4.0000	0.0603	0.0960	0.1921	0.0561	0.2167	0.6273	0.5304
2	alpha	2h	4.0000	0.1245	0.0423	0.0846	0.3020	0.0690	2.9445	0.0032
3	alpha	6h	3.0000	0.2660	0.0558	0.0967	0.4542	0.1367	4.7650	0.0000
4	alpha	8h	4.0000	0.3135	0.0847	0.1695	0.5248	0.0653	3.6995	0.0002
5	alpha	0h	4.0000	0.0948	0.0928	0.1856	0.1691	0.2493	1.0213	0.3071
6	alpha	12h	4.0000	0.2960	0.0623	0.1245	0.4966	0.0862	4.7549	0.0000
7	alpha	1h	4.0000	-0.0683	0.1660	0.3320	-0.4285	0.6604	-0.4111	0.6810
8	alpha	3h	4.0000	0.4858	0.3922	0.7844	0.3579	0.1981	1.2385	0.2155
9	alpha	4h	4.0000	0.3030	0.2753	0.5505	0.3200	0.2905	1.1008	0.2710

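### SAP 6.4.2 judges dose-proportionality from one log-log slope over 5-80 mg without checking that a straight line fits, so a strongly curved exposure profile could average to b near 1 and not be declared a departure.

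*SAP*

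**What the plan says.** The criterion is in SAP 6.4.2. The regression of the log PK parameter "against log Dose represents the power model", and "a 90% confidence interval for the estimate of the slope excluding" b=1 is taken as significant departure. (The formula printed there shows Dose rather than log Dose. I read it as log-log, because only then does b=1 mean proportionality.)

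The same section states that "the 80mg group of PD patients from Part 1 will be included". The analysis schedule in SAP section 7 confirms the set: "including ten 80mg PD patients from Part 1 and forty PD patients (5mg, 10mg, 20mg and 40mg) from Part 2". That is 50 patients, 10 at each of five doses over a 16-fold range.

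SAP 6.4.2 also plans a dose-group ANOVA with Scheffe pairwise comparisons, back-transformed ratios with 95% CIs, plots of the log parameters, and the mean square error, degrees of freedom, F and p for both models. A ratio is called significant if its interval excludes 100%.

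Neither SAP 6.4.2 nor 7.4 contains a lack-of-fit or curvature test, a dose-normalised comparison, or a rule for when the line does not fit. Protocol 6.2 gives as one reason for 10 patients per dose that this number is "adequately supporting potential dose proportionality analyses".

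The earlier human data are in Protocol 3.2: "110, 134, and 2101 ng.h/mL after multiple doses of 20, 40, and 60 mg, respectively", and "24, 144, and 2310 ng.h/mL after a single dose of 20, 40, and 60 mg". The protocol itself describes this increase as disproportionate.

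**The concern.** A single slope summarises dose-proportionality only if the slope is the same over the whole range. If exposure is nearly flat over part of the range and rises steeply over another, the two can average to b near 1. The CI for b then includes 1, and the one stated criterion gives no signal, although exposure is proportional to dose nowhere in the range. The sponsor's own repeat-dose figures have that kind of shape.

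The planned ANOVA does not close the gap. Testing ratios against 100% asks whether two doses give different exposure. A 40-to-80 mg ratio of 200%, which is proportional, and one of 1570%, which is not, could both be declared significant. Nothing in the plan separates them.

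Pharmacokinetics is a primary objective, so the conclusion drawn from this rule will be read as a main result.

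**Working it through.** **Inputs from the documents.** Doses 5, 10, 20, 40 and 80 mg with 10 PD patients each (SAP 6.4.2 and section 7). Rule: 90% CI for b excludes 1 (SAP 6.4.2). Repeat-dose values 110, 134 and 2101 at 20, 40 and 60 mg (Protocol 3.2).

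**Inputs assumed.** The documents give no repeat-dose value at 5, 10 or 80 mg and no between-patient variability. I extend the pilot values in nine ways and use log-SD 0.4 to 0.8. The plan states no slope or precision for this analysis, so there is no figure of its own to reproduce.

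**Local slopes in the pilot.** Slope = ln(exposure ratio) / ln(dose ratio).
- Repeat dose, 20-40 mg: ln(134/110)/ln 2 = 0.28. 40-60 mg: ln(2101/134)/ln 1.5 = 6.79, a 15.7-fold step.
- Single dose: ln(144/24)/ln 2 = 2.58, then ln(2310/144)/ln 1.5 = 6.84.
- One least-squares slope through the three repeat-dose points: 2.43.

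**Slope over the trial's doses.** The doses are equally spaced on the log2 scale. With y the log2 exposure, b = (-2y5 - y10 + y40 + 2y80)/10.

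Worked case: carry the slope of 0.285 down to 5 mg and place the 60 mg value at 80 mg. Exposures are 74, 90, 110, 134 and 2101. Relative to 5 mg, y = 0, 0.285, 0.569, 0.854, 4.825. So b = (0 - 0.285 + 0.854 + 9.650)/10 = 1.02. Exposure per mg is 14.8, 9.0, 5.5, 3.4 and 26.3: it falls about 4.4-fold and then rises about 7.8-fold, yet b is almost exactly 1.

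**All nine extensions.** 20,000 simulated trials per setting; 90% CI from t on 48 df. The range is over log-SD 0.4 to 0.8.

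| Below 20 mg | At 80 mg | b | Rule declares departure |
|---|---|---|---|
| flat | 60 mg value | 0.88 | 5-10% |
| flat | scaled from 60 mg | 0.96 | 0-2% |
| slope 0.285 | 60 mg value | 1.02 | 0-3% |
| slope 0.285 | scaled from 60 mg | 1.11 | 3-8% |
| proportional | 60 mg value | 1.38 | 88-100% |
| flat | 40-60 mg slope carried on | 1.44 | 70-96% |
| proportional | scaled from 60 mg | 1.46 | 96-100% |
| slope 0.285 | 40-60 mg slope carried on | 1.58 | 97-100% |
| proportional | 40-60 mg slope carried on | 1.94 | 100% |

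For comparison, when exposure is truly proportional the rule declares departure in 10% of trials, as a 90% CI must. In the first four rows it does so no more often than that.

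**Fit of the line.** In all nine, the fitted line lies 2.6 to 6.2 times above the assumed 40 mg value and gives 15-44% of the assumed 80 mg value.

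**Lack-of-fit test.** F = [(SSE line - SSE dose groups)/3] / [SSE dose groups/45], where 3 = 5 - 2 and 45 = 50 - 5. At the 5% level it rejects in at least 99% of trials in all nine extensions, and in about 5% when exposure is truly proportional.

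**The case against.** The strongest reply is that b=1.02 is a construction. The pilot has no value at 5, 10 or 80 mg, its own fit gives 2.43, and reaching 1.02 requires a nearly flat 5-40 mg stretch and no rise at all from 60 to 80 mg. The single-dose values, extended in the same way, give b of 1.58 to 2.95, and the rule would flag them in at least 98% of trials. The pilot figures are also weak anchors. They are labelled Cmax but carry ng.h/mL, profiles were fully defined only at 40 and 60 mg, and dosing was four times daily in healthy volunteers for 7 to 10 days, not once daily in patients for about 25. All of this stands, and it is why the point says *could* and gives a range.

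Second, the planned output would make a jump visible. In the b=1.02 case the Scheffe interval for the 40-to-80 mg ratio has a median lower limit of about 880% (log-SD 0.4) to 500% (log-SD 0.8), and it excludes the proportional 200% in 99-100% of trials. This also stands: the information would be there. What is missing is a rule that uses it to judge proportionality.

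Third, Protocol 6.4 makes the assessment optional, and the sponsor already calls the earlier increase disproportionate, so an unexamined claim of proportionality is less likely. That lowers the stakes but does not supply the missing check.

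**Conclusion.** The gap is real and cheap to close. It should be fixed, but it does not invalidate the PK plan. The stated criterion cannot tell proportional exposure from a curved profile whose average slope is near 1, and the only repeat-dose data in the documents suggest that the slope is not constant. Whether the rule would miss the curvature depends on exposures not yet observed: in four of nine extensions it almost always would, and in five it usually would not. These figures rest on the assumed extensions, log-SD 0.4-0.8, 10 evaluable patients per dose, and the pilot shape carrying over to once-daily dosing. The case for the lack-of-fit test does not depend on any one value of b.

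A reader might infer more than the documents support:
- *That this trial would give b of about 1.02.* That is one extension among several.
- *That this is the only formal PK analysis.* The dose-difference ANOVA is also formal. The slope is the only stated criterion for proportionality.
- *That doses will be chosen from the fitted line.* No section says so, and each dose group is reported in its own right.
- *That the SAP equates a CI including 1 with proven proportionality.* It says only that exclusion indicates departure. The risk lies in how a non-exclusion is read.

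**What to change.** In SAP 6.4.2, for Cmax and each AUC:

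1. Test lack of fit of the log-dose line against the dose-group ANOVA already planned (F on 3 and 45 df with 50 evaluable patients; adjust if fewer), at a stated level.
2. Interpret b and its 90% CI as the summary of proportionality only when there is no evidence of lack of fit.
3. Otherwise report dose-normalised geometric means with CIs for each dose and slopes for sub-ranges such as 5-40 and 40-80 mg, and do not conclude that there is no departure from b alone.
4. Correct the printed formula to log Dose, so that b=1 has its intended meaning.

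Cost: one extra F test from two models already being fitted, plus SAP wording. No new data are needed. SAP 6.4 defers all PK analysis until Part 2 is complete, so the rule can be set before the PK results are seen.
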